6.5 Quality of Life Evaluation

Measuring quality of life (QOL) outcomes in cancer patients has become an important mandate for clinical trials. It is especially important to assess QOL in phase II cancer clinical trials that are likely to

Proprietary of MD Anderson Cancer Center

move into the phase III setting. The extent to which treatment impairs QOL is information the patients need when making treatment decisions. It is also important to try and identify factors that are associated with better adjustment to help us identify patients at risk for adjustment problems and translate this information into the clinical setting to individualize intervention programs. In addition, elucidating protective and risk factors will help identify individuals at greater risk for medical complications, disease progression, and recurrence.

Patients will experience somewhat different symptoms when they receive the different therapies. In order to assess the effects of combining these treatments, we will assess multidimensional aspects of QOL over the treatment course.

QOL evaluations will not be performed during the long term extension phase of the trial.

6.5.1 Assessment Schedule

All patients will complete a full assessment battery at baseline, *prior* to treatment. Patients will then complete a brief assessment battery at week 2, week 4, week 6, and then every 12 weeks (see Table 4).

Table 4: Data collection sessions for psychosocial measures

BASELINE	FOLLOW-UP

 • FACT • SF-12 • Depression (CES-D) • Social Provisions Scale • History of depression • FMCS 	
 • FACT • SF-12 • CES-D • FMCS

Several measures used previously in our work on chronic stress and QOL will be used in the proposed study. In all cases, they have proven to be useful and sensitive measures of stress and QOL, have proven to be stable, reliable, and valid with groups of people who are and are not suffering from major depression or other psychiatric disorders. All surveys will be completed electronically using e-tablets and response data will be collected using the HIPAA-compliant Qualtrics software platform.

Quality of Life:

The Functional Assessment of Cancer Therapy (FACT) is a cancer-specific measure of *health-related quality of life*. This instrument was able to discriminate between individuals with metastatic and non-metastatic disease, as well as between patients at different stages of illness. The scale has been found to have good concurrent validity, high internal consistency (0.89), and good test re-test reliability (0.82 to 0.88). The FACT will be completed at each assessment.

General QOL – General QOL will be assessed using the Medical Outcomes Study 12-item short-form survey (SF-12). Responses are based on a Likert-type scale. The SF-12 is a health-related QOL measure that is responsive to minor versus major medical problems as well as psychiatric problems. It has good test-retest reliability (coefficients for various subscales range from 0.60 to 0.81) and good internal consistency (coefficients range from 0.78 to 0.93). The SF-12 will be completed at each assessment.

Proprietary of MD Anderson Cancer Center

Depression:

Depression will be assessed using the Centers for Epidemiologic Studies - Depression (CES-D) (3). The CES-D is a well-validated 20-item self-report measure of depression that focuses on affective components of depression. Cut-off scores of 16 for screening clinical depression have been recommended. Internal consistency is high in the general population and in patient populations. It also has been demonstrated to possess adequate convergent validity with other measures of depression. The CES-D will be completed at baseline and at each subsequent assessment.

Lifetime history of Major Depressive Disorder (MDD) will be measured using the two cardinal items from the Structured Clinical Interview for DSM-IV Disorder (SCID) that assess lifetime presence of depressed mood or anhedonia for two weeks or more. Patients are considered to have lifetime MDD if they endorse one or both of the items. These two questions will only be completed at the first assessment.

Social Support:

Perceived availability of social support will be measured using the 24-item Social Provisions Scale that includes subscales for attachment, social integration, opportunity for nurturance, reassurance of worth, reliable alliance, and guidance. The SPS will only be completed at baseline.

Hope for the future:

Finding meaning in cancer will be measured using the Finding Meaning in Cancer scale (FMCS). This 17-item scale assesses benefits in different domains, including accepting life's imperfections, changing priorities, and developing a sense of purpose in life. The scale is scored as a single factor, has good internal consistency (0.95), and has shown moderate association with psychological well-being.

7.0 CORRELATIVE STUDIES

We will perform immune monitoring, including but not limited to the evaluation of CD4 and CD8 T cells in available tumor tissue and peripheral blood samples as previously published.⁶³⁻⁶⁶ Peripheral blood and tumor tissue samples (optional) will be obtained within 14 days pretreatment, 2 weeks after MGCD516 monotherapy, following 2 infusions of Nivolumab, and upon disease progression. All samples will be collected and analyzed per a separate IRB-approved protocol. In addition, another IRB-approved protocol, separate from the aforementioned immunotherapy analyses, will be used to investigate in the blood and tumor tissues, a panel of cytokines, chemokines, cell-free DNA, and other relevant angiogenic factors, biological receptors, ligands, nucleotides and proteins.

Up to one hundred (150) ml of blood will be drawn at the visits outlined in Sections 9 and 10. These samples will be labeled with confidential identification numbers and provided to the Immunotherapy platform for immunological assessments. A detailed laboratory manual highlighting the blood collection and processing procedures will be prepared. All blood collection will be compliant with institutional safety standards and will not exceed the maximum blood draw per venipuncture policy.

Blood and tissue collections for correlative studies will not be performed during the long term extension phase of the trial. The only exception is optional collection of blood or tissue samples for those patients taken off therapy due to disease progression to assess causes of disease progression.

8.0 DISCONTINUATION OF THERAPY

Patients MUST be discontinued from study therapy AND withdrawn from the study for the following reasons:

- Withdrawal of informed consent (subject's decision to withdraw for any reason)
- Any clinical adverse event, laboratory abnormality or intercurrent illness which, in the opinion of the Investigator, indicates that continued treatment with study therapies is not in the best interest of the subject
- Termination of the study by MD Anderson Cancer Center
- Imprisonment or the compulsory detention for treatment of either a psychiatric or physical (e.g., infectious disease) illness.
- Progressive disease: Patients, who develop rapidly progressive disease (clinically or by RECIST) before the scheduled evaluations, may be taken off protocol treatment at the discretion of the investigator. Patients can continue to receive their assigned targeted agent, even if they develop progressive disease radiographically, as long as in the judgment of the treating physician, they are benefitting from their targeted agent.

Patients whose treatment is interrupted or permanently discontinued due to an adverse event or abnormal laboratory value suspected to be related to study drug must be followed at least weekly until the adverse event or abnormal laboratory resolves or returns to grade 1. This may be done by telephone correspondence. If a patient requires a dose delay of > 28 days from the intended day of the next scheduled dose, then the patient must be discontinued from the study. If one agent (MGCD516 or nivolumab) is interrupted or discontinued, administration of the other agent may continue at the discretion of the Investigator and patient.

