Dosing interruptions > 4 weeks that occur for non-drug-related reasons may be allowed if approved by the Principal Investigator. Prior to re-initiating treatment in a subject with a dosing interruption lasting > 4

Proprietary of MD Anderson Cancer Center

weeks, the UTMDACC IND Office must be notified. Tumor assessments should continue as per protocol even if dosing is interrupted.

As described above, after the patient has received at least 2 infusions of nivolumab and 6 weeks (42 days) of oral MGCD516 then further combination treatment can be held for up to 4 weeks (28 days) to allow for recovery from surgery, radiation therapy, or other interventions for palliation purposes or management of intercurrent illness which, in the judgement of the treating physician, is not related to disease progression.

Immune-related Adverse Events (irAEs) are defined in the nivolumab label as those occurring during nivolumab therapy, often necessitate immunosuppression and have no other alternate etiology. The nivolumab package insert (http://packageinserts.bms.com/pi/pi_opdivo.pdf) provides detailed evaluation and management guidelines for the following types of ir-AEs: pneumonitis, colitis, hepatitis, endocrinopathies, nephritis/renal dysfunction, rash, and encephalitis. As a general principle, nivolumab should be withheld or permanently discontinued in patients with moderate or severe irAEs. Depending on the nature of the irAE, it should be managed with corticosteroids and/or hormone-replacement therapy. The corticosteroids should be tapered down upon improvement of the irAE to Grade ≤ 1 . Depending on the severity of the irAE, restarting of nivolumab may be considered. Prior to re-initiating treatment in a subject with a dosing interruption lasting > 28 days, the UT MDACC IND Office must be consulted. Tumor assessments should continue as per protocol even if dosing is interrupted.

Patients experiencing any Grade 4 non-hematological toxicity should be taken off study. MGCD516 can be held in patients experiencing, despite optimal supportive care, persistent non-overlapping toxicities attributed to MGCD516, such as hypertension, palmar-plantar erythrodysesthesia, peripheral neuropathy, or stomatitis. The Principal Investigator must be consulted prior to re-initiating treatment in a subject with a dosing interruption lasting > 4 weeks.

With regards to the management of potential overlapping toxicities of the two drugs:

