- Patients experiencing Grade 3 fatigue for > 5 days despite optimal supportive care should be taken off study with discontinuation of the combination therapy.
- In patients experiencing Grade 3 rash or Grade 2/3 diarrhea, both oral MGCD516 and nivolumab should be held until improvement to Grade ≤ 1 . Topical and/or systemic steroids can be given as needed. If no improvement to \leq Grade 1 after combination treatment has been held for > 3 weeks then the patient should be taken off study. Dosing interruptions for prolonged steroid tapers > 6 weeks to manage drug-related adverse events are allowed. The Principal Investigator must be consulted prior to re-initiating treatment in a patient with a dosing interruption lasting > 4 weeks.
- Patients experiencing Grade 3/4 elevation in serum amylase and/or lipase levels associated with clinical or radiological evidence of pancreatitis, with no other alternate etiology, should be taken off study with discontinuation of the combination therapy.

Discontinuation criteria for nivolumab and MGCD516 are described in sections 8.1 and 8.2, respectively.

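### Section 8.0 makes a toxicity stop, or any dose delay over 28 days, an exit from the study, against the follow-up and restart rules in other sections

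*Combined protocol and SAP*

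**What the plan says.** Section 8.0 opens its list of reasons with "Patients MUST be discontinued from study therapy AND withdrawn from the study for the following reasons". One reason is an adverse event, laboratory abnormality or intercurrent illness that, in the investigator's view, makes continuing the study therapies contrary to the patient's interest. Later in 8.0, if the next scheduled dose is delayed by more than 28 days, "then the patient must be discontinued from the study". No exception is given. Section 12.0 closes by saying that once a patient is withdrawn from the study, nothing further is collected or added to any database.

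Section 8.0 also says that patients whose treatment is interrupted or permanently stopped for a suspected drug-related event "must be followed at least weekly until the adverse event or abnormal laboratory resolves or returns to grade 1". If only one agent is interrupted or stopped, "administration of the other agent may continue at the discretion of the Investigator and patient".

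Section 6.4 handles long interruptions differently. For immune-related events it says "Prior to re-initiating treatment in a subject with a dosing interruption lasting > 28 days, the UT MDACC IND Office must be consulted". In the rash and diarrhea bullet it says "Dosing interruptions for prolonged steroid tapers > 6 weeks to manage drug-related adverse events are allowed". Non-drug-related interruptions beyond 4 weeks may go ahead with the Principal Investigator's approval. Section 8.1 repeats the taper and non-drug exceptions for nivolumab. Section 6.4 also uses off-study language for some toxicities: "Patients experiencing any Grade 4 non-hematological toxicity should be taken off study". For prolonged Grade 3 fatigue, and for amylase or lipase elevation with pancreatitis, patients "should be taken off study with discontinuation of the combination therapy".

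**The concern.** Stopping a drug and leaving a trial are different events with different consequences for the data. A patient who stops for toxicity should normally remain under observation for safety and survival. Section 8.0 joins the two events with a mandatory AND, and section 12.0 attaches the end of data collection to the second.

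Overall survival (OS) and progression-free survival (PFS) are secondary objectives, and section 3.4 reports that median OS had not been reached. Ending survival contact at a toxicity stop would lose later deaths for a reason that may be related to prognosis. It would also cut short the adverse-event follow-up that the protocol requires.

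The 28-day sentence raises a separate operational problem. A patient on a steroid taper that 6.4 permits could not restart, although 6.4 describes the consultation to hold before restarting.

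**Working it through.** No design figure depends on this point, so the check sets the rules side by side.

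**Step 1. Stopping for an adverse event**

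| Place | What happens to the patient |
|---|---|
| 8.0, lead sentence and adverse-event bullet | Off therapy and withdrawn from the study (mandatory) |
| 12.0, last sentence | Study withdrawal ends data collection |
| 8.0, later paragraph | At least weekly follow-up until the event resolves or returns to grade 1 |
| 8.2 | Adverse event appears among reasons to stop medication, not among the examples for ending follow-up; data collection stops when consent to disclosure is also withdrawn |
| 10.8 and calendar footnote k | Survival follow-up every 3 months (every 6 months for patients in long-term follow-up when the extension is approved), with no exclusion for adverse events |
| 12.0, bullet | Unacceptable adverse event: removal from protocol treatment |
| 13.1 | Adverse events evaluated until 4 weeks after treatment stops |
| 13.2 | Serious events captured until 30 days after the last dose unless consent is withdrawn; related ones reported after that |

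The first two rows together end data collection at the stop. The other rows require it to continue, so they cannot all be followed as written. The progression bullet under the same lead sentence only permits removal from treatment, and allows continuation. The lead sentence therefore does not fit its own list, which points to a drafting slip.

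**Step 2. Delay of more than 28 days**

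| Place | Rule |
|---|---|
| 8.0 | Off the study, no exception; whether it applies to each agent separately is not stated |
| 6.4, immune-related events | Restart possible after consulting the IND Office |
| 6.4, rash and diarrhea bullet | Taper interruptions over 6 weeks allowed |
| 6.4, non-drug reasons | Over 4 weeks allowed with Principal Investigator approval; not limited to one agent |
| 8.1, nivolumab | Over 4 weeks means discontinuing nivolumab, except for tapers and approved non-drug reasons |
| 12.0, bullet | Toxicity delay over 4 weeks: removal from treatment only, no taper exception |

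If 8.0 governs, the restart provisions in 6.4 and 8.1 for delays over 28 days have no function.

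**Step 3. Scale, from section 3.4**

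- Stopped for adverse events: 4/42 = 9.5%, as stated there.
- High-dose glucocorticoids for immune-related events: 8/42 = 19.0%, as stated there. This is a group in whom long tapers could arise. It does not count delays, and it does not bound them, because the non-drug exceptions are separate.
- Delayed more than 28 days: not given.
- Still on treatment at cutoff: 12/42 = 28.6%, as stated there.

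**The case against.** The strongest reply is that a general rule should be read with its specific exceptions. Section 8.1 sits under 8.0 and sets out the exceptions for nivolumab, and 6.4 gives similar permissions. Experienced staff would probably apply them. The safety windows in 13.1 and 13.2, and the request in 10.7 for imaging when toxicity stops treatment before restaging, also indicate that coming off therapy was not meant to end observation. This is fair as to intent and explains why the matter is modest. It does not repair the text: 8.0 refers to none of these exceptions, its wording is mandatory, and 8.1 covers one drug only.

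Four narrower objections stand and limit the point:

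- The adverse-event bullet concerns stopping the study therapies as a whole. It does not reach every patient who stops one agent, since 8.0 lets the other continue. Section 3.4 does not say whether the 4 patients stopped one agent or both.
- Section 12.0 shares the 4-week limit for toxicity delays. It differs in consequence (treatment rather than study) and in lacking the taper exception. Its closing sentence can also be read as covering only patients who choose to withdraw.
- The off-study wording in 6.4 agrees with 8.0 if taken literally, so 6.4 is not uniformly on the other side.
- The list in 8.2 of reasons for ending follow-up is introduced as non-exhaustive, so the absence of adverse events from it is supportive rather than decisive.

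**Conclusion.** The inconsistency is real and is a wrong stated rule rather than missing detail. Read literally with 12.0, section 8.0 ends survival and safety data after a toxicity stop of the study therapies. Its 28-day sentence bars restarts that 6.4 and 8.1 provide for. This rests on giving the lead sentence of 8.0 and the last sentence of 12.0 their plain meaning.

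The documented exposure is 4/42 patients (9.5%) stopped for adverse events, plus an unknown number delayed over 28 days. The remaining effect is limited: 12/42 patients were on treatment at cutoff, section 10.9 governs those who enter the extension, and survival contact is by record review or telephone. It is worth correcting, but not urgent.

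Two stronger conclusions are tempting. A reader might infer that the reported OS or PFS is biased. The documents do not show that any patient was lost under this rule, so neither size nor direction can be given. A reader might instead infer from the survival count that the literal rule was never applied: 34 alive less 12 on treatment leaves 22 off treatment and alive. But 25 patients stopped for progression, so all 22 could come from that group. The count says nothing about the 4 adverse-event stops.

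No effect on dose selection is claimed; it rests on toxicity within 12 weeks and efficacy within 6 weeks.

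**What to change.** Amend the wording as follows.

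1. In 8.0, make the lead sentence a rule for stopping study therapy. Reserve withdrawal from the study for withdrawn consent to follow-up and for study termination. The sponsor decides whether detention stays as a reason for withdrawal.
2. In 6.4, define the off-study wording as off therapy.
3. In 12.0, limit the closing sentence on data collection to true study withdrawals, in line with 8.2, and state that all other patients remain in survival follow-up under 10.8.
4. In 8.0, change the 28-day sentence to discontinuation of treatment and say whether it applies to each agent separately. Write the 6.4 and 8.1 exceptions into it and into the delay bullet in 12.0.

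The cost is one wording amendment and the decision on detained patients. It adds no visits, tests or patients, because survival follow-up, the safety windows and the restart consultations are already in the protocol.

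### Sections 8.0 and 12.0, read literally, end survival and safety follow-up after an adverse-event stop and remove patients whom 6.4 and 8.1 allow to resume

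*Combined protocol and SAP*

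**What the plan says.** Section 8.0 ties two actions together: "Patients MUST be discontinued from study therapy AND withdrawn from the study for the following reasons". One listed reason is "Any clinical adverse event, laboratory abnormality or intercurrent illness which, in the opinion of the Investigator", makes further treatment contrary to the patient's interest. Progression is listed under the same heading, but its wording is permissive: patients with rapid progression before a scheduled evaluation "may be taken off protocol treatment at the discretion of the investigator", and others may carry on.

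The paragraph after the list says that a patient whose treatment is interrupted or permanently stopped for a suspected drug-related event "must be followed at least weekly until the adverse event or abnormal laboratory resolves or returns to grade 1". It then says that if a dose is delayed by more than 28 days, "then the patient must be discontinued from the study", with no exception.

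Section 12.0 states that once a patient is withdrawn from the study, no new information is collected. It does not restrict this to patients who withdraw consent.

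Other sections set different rules:

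- Section 6.4: "Dosing interruptions > 4 weeks that occur for non-drug-related reasons may be allowed if approved by the Principal Investigator", and "Dosing interruptions for prolonged steroid tapers > 6 weeks to manage drug-related adverse events are allowed". Section 8.1 has matching exceptions for nivolumab.
- Section 6.4 also uses study-removal language for toxicity: "Patients experiencing any Grade 4 non-hematological toxicity should be taken off study".
- Section 8.2 lists separate reasons for leaving follow-up, and neither progression nor adverse events is among them. It ends data collection only when consent to disclosure is also withdrawn.
- Section 10.8 and calendar footnote k schedule survival contact every 3 months. Sections 13.1 and 13.2 collect adverse events to 4 weeks after treatment and serious adverse events to 30 days after the last dose.

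**The concern.** Stopping treatment and leaving the study are different events, and 8.0 merges them for adverse events. With the sentence in 12.0, a coordinator who follows the text would stop collecting data on a patient at the point of a toxicity stop, when safety follow-up matters most.

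Overall survival is a secondary objective, to be estimated by Kaplan-Meier. Patients who leave because of toxicity are likely to differ in risk of death from those who stay. Censoring them on leaving would therefore be informative, and if their risk is higher the survival curve would tend to sit too high. The wording still matters after enrollment because median survival had not been reached at the cutoff, so the estimate depends on follow-up off treatment.

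The unqualified 28-day rule is a second problem: it removes from the study patients whom 6.4 and 8.1 expressly allow to resume.

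**Working it through.** **Comparison of the rules**

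| Situation | 8.0 (with 12.0) | Elsewhere |
|---|---|---|
| Stop for an adverse event | Withdrawn from the study; no new data | Weekly follow-up (8.0); survival contact (10.8, footnote k); safety windows (13.1, 13.2); data end only with withdrawn consent (8.2) |
| Delay over 28 days | Off the study, no exception | Longer gaps allowed for steroid tapers and non-drug reasons (6.4, 8.1); a toxicity delay over 4 weeks is removal from treatment only (12.0) |
| Progression | Under the MUST heading, but discretionary and about protocol treatment only | Follow-up continues (8.2, 10.8); treatment past progression governed by 8.3 |

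The first two rows are direct conflicts. The third is a mismatch between a mandatory heading and a permissive bullet.

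**Scale, from section 3.4**

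Inputs: 42 enrolled; 12 still on treatment; 25 stopped for progression; 4 stopped for adverse events; 34 alive; one toxicity death. Section 3.4 prints 80.1% for 34/42, but 34 / 42 = 81.0%, so the count is used.

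- Off treatment: 42 − 12 = 30. Other reason: 30 − 25 − 4 = 1.
- Not alive: 42 − 34 = 8. Alive off treatment: 34 − 12 = 22.

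*Clearly mandatory rule (adverse-event stops).* 4 / 42 = 9.5%. The 8 deaths fall among 25 + 4 + 1 = 30 stops. The 25 + 1 = 26 stops not due to adverse events could hold all 8 deaths, so the minimum among adverse-event stops is 0. The maximum is 4. The range is 0 to 4 of the 8 deaths.

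*Ceiling (every progression stop also counted as a withdrawal).* 25 + 4 = 29, and 29 / 42 = 69.0%. Deaths among these are 8 − 1 = 7 if the one other patient died, or 8 if not. Leaving out the toxicity death, which may have come before any withdrawal, 6 or 7 could be missed. Living patients censored on leaving would number 29 − 8 = 21 or 29 − 7 = 22.

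The documents do not report how many patients had a delay over 28 days, so that conflict cannot be sized.

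**The case against.** The strongest reply is that the rest of the protocol shows what was meant. Section 12.0 is headed as criteria for removal from protocol treatment, and it lists the patient's decision to withdraw separately from progression and adverse events. Its sentence on withdrawal can be read as belonging to that decision alone, which would agree with 8.2. The calendar places long-term follow-up in the end-of-treatment column, 10.8 makes provision for patients in long-term follow-up when the extension is approved, and 10.7 provides for samples after removal for progression. The 22 patients reported alive off treatment suggest that 10.8 was followed in practice.

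Most of this stands as evidence of intent. It does not remove the conflict. The sentence in 12.0 carries no such limit, 8.0 uses the language of study withdrawal for adverse events, and the 28-day rule in 8.0 has no exception.

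Three stronger readings are not supported:

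- A reader might infer that all 29 progression and adverse-event stops had to be withdrawn. The progression bullet is permissive, its removal wording covers only rapid progression before a scheduled evaluation, and it concerns protocol treatment. Section 3.4 does not say how many of the 25 fit that description.
- A reader might infer that reported survival is already biased. Nothing in the documents shows lost follow-up.
- A reader might infer that the shorter progression bullets in 8.0, 8.2 and 12.0 permit treatment past progression outside 8.3. Section 8.3 covers all such decisions, and 5.3 points to it. It also dates progression at the initial event, so PFS is unaffected.

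**Conclusion.** The inconsistency is real and minor. Two rules, applied as written, lead to a wrong action: ending survival and safety follow-up after an adverse-event stop, and removing from the study patients whose longer interruption is allowed elsewhere. It is a conflict between stated rules, not a questionable design choice.

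The size to carry forward is 4 of 42 patients and 0 to 4 of the 8 deaths; 29 of 42 is a ceiling, not an estimate. These figures are the reach of a literal reading, not an observed loss. They assume that the 25 and the 4 do not overlap, that all 8 patients not counted as alive had died and none was lost to follow-up, and that each adverse-event stop came under the investigator-judgment bullet. The counts of possibly missed deaths further assume that death followed the stop. Overall survival is secondary and has no decision rule attached, which also keeps the severity low.

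**What to change.** - **8.0, list.** Keep study withdrawal only for withdrawn consent, study termination, and imprisonment or detention. Put adverse events under *must be discontinued from study therapy*. Put progression in a separate line under *may be discontinued from study therapy*, so that MUST no longer governs it.
- **8.0, delay rule.** Make a delay over 28 days a discontinuation of study therapy, *except as allowed in 6.4 and 8.1*.
- **8.0, new sentence.** State that patients who stop therapy for these reasons remain in survival follow-up (10.8) and safety follow-up (13.1, 13.2).
- **6.4.** Change *taken off study* to *taken off study therapy* wherever it is used for toxicity.
- **12.0.** Limit the sentence on no new information to patients who withdraw consent for further data, as in 8.2.
- **8.0, 8.2 and 12.0, progression bullets.** Add *as described in Section 8.3*. This is a cross-reference only; the extension phase keeps its own rule (10.9, 11.6).

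The cost is one wording amendment to four sections. It adds no visits, data or analyses.
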